### **2.2. Aim**

To investigate whether a Verbal Health Literacy training session for staff, with accompanying tailored support from a Health Literacy Officer to help implement the techniques into practice, can improve health outcomes for patients.

### **2.3. Objectives**

- a) To understand staff perceptions of the acceptability and feasibility of the Verbal Health Literacy training session, and the support to use the techniques in practice from the Health Literacy Officer.
- b) To understand staff knowledge of the Verbal Health Literacy techniques and their confidence and skills to use them.
- c) To understand how the Verbal Health Literacy techniques taught in the training session are being actioned in practice.
- d) To determine whether subjective Health Literacy and activation skills, such as the ability to self-manage, engage with healthcare services and understand what actions to take, are improved for service users after attending programmes delivered by Verbal Health Literacy trained members of staff.
- e) To measure the impact of the Verbal Health Literacy training on health and wellbeing outcomes.
- f) To describe the Index of Multiple Deprivation quintile of attendees at programmes and compare with the Derbyshire population in order to assess impact on health inequalities.

### **3.Plan of investigation**

#### **3.1 Design**

The objectives will be achieved through a mixed methods evaluation. This will consist of a process evaluation to assess acceptability, feasibility and use of the learnt techniques in practice (Moore *et al.*, 2015), and a concurrent pre-test post-test measurement of outcomes, or controlled pre-test post-test measurement of outcomes where possible (Aggarwal & Ranganathan, 2019; NICE, 2012).

#### **3.2 Timing of intervention**

For both programmes staff will receive Verbal Health Literacy training and implementation support from the Health Literacy Officer. Outcomes will be measured for service users joining a programme run by trained staff. Where appropriate and for comparison, outcomes will be measured for service users joining a programme run by non-trained staff during the same period.

Half of the staff from the weight management programme (4/8) will receive the training to allow for controlled before and after comparison of outcomes. One member of staff takes a group of service users through their weight management sessions so it will be possible to identify service users linked to trained and untrained staff. This is not possible for the pulmonary rehabilitation service where different staff work with different service users throughout the programme. All six physiotherapists and two specialist nurses from the pulmonary rehabilitation service will receive the training. The focus is on physiotherapists and specialist nurses because they spend most time with service users.

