#### 1.3.6 The services where the intervention will be used

The intervention will be used in two very different services.

1. Live Life Better Derbyshire tier 2 weight management services (Public Health, Derbyshire County Council). The aim of the programme is to help people lose weight. The service provides online and face to face group education and advice programmes that run for one session a week over a rolling 12 week period. The programmes have an accompanying website and resources. The

programme is available for all people in Derbyshire. Eight Public Health Improvement Advisors (HIA's) offer advice to groups of up to 25 people who need to lose weight. 33 programmes run across Derbyshire, 19 online and 14 face to face. Attenders are followed up at 12, 26 and 52 weeks and a weight maintenance programme is available.

2. Derbyshire Community Health Service Pulmonary Rehabilitation programme provided within the NHS. The aim of the programme is to improve people's exercise tolerance and respiratory health. This service provides a six week rolling face to face programme that runs across 6 venues in Derbyshire. 15 members of staff, a mixture of physiotherapists, healthcare assistants and specialist nurses, offer supervised exercise and education and advice to people who are limited by their respiratory condition in Derbyshire. The physiotherapists and specialist nurses lead the sessions and have most contact with patients. Up to 12 people attend two sessions a week over the six week period which are a combination of exercise and education.

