### **3.9 Sampling strategy and sample size**

#### **3.9.1. Staff**

There are currently eight staff that deliver the weight management programme. There are currently six physiotherapists and two specialist nurses who deliver the

pulmonary rehabilitation programme. Four out of the eight weight management programme staff will receive the Verbal Health Literacy training. Six physiotherapists and two specialist nurses from the pulmonary rehabilitation programme will receive the training. All staff from the two participating services who receive the training, n=12, and from the wider services who complete the training during the study period, will be asked to complete the three questionnaires.

All trained staff, from each of the two services (n=12) where possible, will be observed pre and post the intervention and be part of the focus groups.

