#### LLBD Weight Management Programme sample size calculation

From January to March 2023 the mean starting weight was 103.68kg. The mean weight on completion of the 12 week course was 99.60kg. So, the mean weight loss was 4.08 kg for this cohort. This was larger than the mean weight loss of 2.3 kg for behavioural weight management interventions in primary care at 12 months compared with controls (Madigan *et al*, 2022). But people can gain weight after initial loss so we are happy to use the historical Derbyshire data to help calculate a required sample size.

We expect the mean weight loss for the Derbyshire service to be larger in 2024 than in early 2023 potentially due to the health literacy training but also likely to be related to improvements management have made to the service between 2023 and 2024.

We would expect a minimum of a 10% increase in the mean weight loss in the trained group vs. untrained group at 12 weeks, that is, 4.7kg vs. 4.3kg. With an estimated pooled standard deviation of 1.6, a sample size of 252 would be required in each group to detect this size of difference with 80% power at a 5% level of significance. As stated earlier there will be approximately 330 service users in each group who can be invited to take part. We therefore should be able to recruit sufficient numbers (252) to ensure we will be able to detect an improvement in weight loss over time at a service level.

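### The protocol does not say how the four trained weight-management advisers are chosen or whether delivery mode is balanced, so the individual-level comparison cannot separate training from pre-existing adviser or mode differences

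*Combined protocol and SAP*

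**What the plan says.** - Section 3.1 describes the design as "controlled pre-test post-test measurement of outcomes where possible". Randomisation is not mentioned.
- Section 3.2: "Half of the staff from the weight management programme (4/8) will receive the training". The reason given is to have a control for a before-and-after comparison. Section 3.9.1 repeats the number: "Four out of the eight weight management programme staff will receive the Verbal Health Literacy training". Neither gives a selection method. Section 3.8.2 says only that service leads help with staff recruitment.
- Section 3.2 also fixes the unit of exposure: "One member of staff takes a group of service users through their weight management sessions".
- Section 1.3.6: "33 programmes run across Derbyshire, 19 online and 14 face to face". The split of these programmes by adviser is not given.
- Section 3.8 recruits service users who enrol after their adviser has, or has not, been trained.
- Section 3.10.4 plans a multiple regression of baseline-to-12-week change, trained against untrained, and names no covariates.
- Sections 3.7 and 3.10.5 plan aggregate before and after data for both groups, without individual records.
- The sample size under 3.9.3 rests on mean losses at 12 weeks, "that is, 4.7kg vs. 4.3kg", "With an estimated pooled standard deviation of 1.6", "with 80% power at a 5% level of significance".

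**The concern.** This is the only concurrent controlled comparison in the study, and it sets four advisers against four. If the trained four differ beforehand in skill, enthusiasm, caseload or online share, every service user in their groups carries that difference.

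At individual level nothing in the plan would remove it. The baseline is each user's own starting weight, taken after the adviser's training status is settled. A user's 12-week change is therefore already the adviser's result under the assigned condition. Adjusting for baseline weight or demographics does not touch an adviser-level difference.

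It would also be hard to see. The pre-training observations (3.4) cover only staff who will be trained, and the baseline questionnaire (3.3.1) goes only to those attending training. Quality Conversations training is already open to all staff (1.3.1), so prior communication skill may differ between advisers.

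**Working it through.** **1. The plan's own figure.** Difference 4.7 - 4.3 = 0.4 kg, SD 1.6 kg, 80% power, two-sided 5% (sidedness is not stated, but two-sided reproduces the figure):

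n per group = 2 x (1.960 + 0.842)^2 x 1.6^2 / 0.4^2 = 2 x 7.849 x 16 = 251.2, rounded up to 252. This matches the protocol. The effect sought is 0.4/1.6 = 0.25 SD.

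**2. Adviser selection.** The between-adviser SD of mean 12-week loss is not in the documents. Assumption: 0.2-0.4 kg, which as an intraclass correlation is 0.2^2/1.6^2 = 0.016 to 0.4^2/1.6^2 = 0.063.

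For eight normally distributed advisers, the expected mean of the top four minus that of the bottom four is 1.449 adviser SDs (simulation). If selection correlates r with performance, the expected gap is r x 1.449 x SD.

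| Selection (assumed) | SD 0.2 kg | SD 0.4 kg | Share of 0.4 kg |
|---|---|---|---|
| r = 0.3 | 0.09 kg | 0.17 kg | 22-43% |
| r = 0.5 | 0.14 kg | 0.29 kg | 36-72% |
| best four (r = 1) | 0.29 kg | 0.58 kg | 72-145% |

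Even when the best four are chosen, the gap reaches 0.4 kg only at an adviser SD of 0.4/1.449 = 0.28 kg.

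**3. Delivery mode.** Bias = difference in online share x difference in mean loss between modes. Neither factor is given. Assume 33/2 = 16.5 programmes per group:
- 14 online against 5: shares differ by 9/16.5 = 55 points, so a mode difference of 0.4/0.545 = 0.73 kg would produce 0.4 kg.
- 12 against 7: 5/16.5 = 30 points, and 0.4/0.303 = 1.32 kg would be needed.

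**4. What a random draw leaves.** The chance gap between two groups of four has SD = adviser SD x sqrt(1/4 + 1/4) = 0.707 x adviser SD, that is 0.14-0.28 kg under the same assumption. A gap of at least 0.4 kg in either direction then has probability 0.5% at SD 0.2 kg and 16% at SD 0.4 kg. Its expected value is zero, unlike the gaps in step 2.

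**The case against.** The strongest reply is that the design already has a control for this. Sections 3.7 and 3.10.5 obtain before and after data for trained and untrained groups, and the 0.4 kg target sits under the service-level heading (3.9.3), where those data exist. Pre-period data of this kind are how a controlled before-and-after study exposes stable adviser or mode differences. That stands in part. It would be wrong to infer that any pre-existing difference must be reported as a training effect throughout the study: that applies to the regression in 3.10.4, not necessarily to the service-level analysis. But the text does not say that the earlier period is divided by the same advisers, and no difference-in-differences estimate is named. The sample size is built on a simple trained-against-untrained difference. It also expects management improvements between 2023 and 2024, which may not affect all advisers or modes equally.

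Three further inferences are tempting but not supported:
- *That the four are known to be volunteers, manager-chosen or otherwise not random.* The documents are silent; they neither state nor exclude a random draw.
- *That the bias is as large as the effect sought.* This needs an adviser SD or mode difference that the documents do not give, together with adverse selection. At a correlation of 0.5 the gap stays at 36-72% of the target.
- *That a random draw brings a usable exact permutation test.* An unrestricted draw has C(8,4) = 70 allocations and a smallest two-sided p of 2/70 = 0.029. Two strata of four leave 6 x 6 = 36 (p 0.056) and four pairs leave 2^4 = 16 (p 0.125). A balanced draw of either kind cannot reach 0.05 this way.

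It is also fair to say that advisers may not have a main mode: 33/8 is about four programmes each, possibly mixed.

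**Conclusion.** The concern holds as a gap in the plan: the selection method and the balance on delivery mode are not stated, and the individual-level comparison has no means of separating training from what the advisers brought with them. At service level the gap is partly closed if the earlier data are split by the same advisers and used as a difference in differences; the text commits to neither.

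The size of the bias cannot be derived from the documents. Under an assumed adviser SD of 0.2-0.4 kg it would be a substantial share of the 0.4 kg target with moderate selection. It would match or exceed the target only if selection came close to picking the best four and the adviser SD was towards the upper part of that range, or if a mode imbalance were added. This is worth correcting before training starts, because it concerns who is trained and cannot be repaired in the analysis.

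**What to change.** - **Sections 3.2 and 3.9.1.** If the choice is still open, draw the four advisers by lot before the pre-training observations (June-July 2024 in section 6), balanced on delivery mode where advisers have a main mode. If they are already chosen, state how, and report delivery mode and pre-training mean weight loss for the trained and untrained groups.
- **Section 3.10.4.** Add delivery mode as a covariate. This helps only if both modes occur in both groups, which is a further reason to balance the draw. Section 3.5 does not list mode among the data to be shared, so the request needs that field.
- **Section 3.10.5.** Split the pre-period by the same advisers, and name the between-group difference in before/after change as the service-level estimate.

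**Cost.** A short draw, a few sentences and one data field. The service loses free choice of who is trained first; the other four can be trained after data collection. The difference-in-differences estimate is less precise: with equal periods and independent users its variance is double that of a single difference, so 0.4 kg would need 2 x 251.2 = 502.3, about 503 per group in each period, against the roughly 330 per group cited under 3.9.3. Section 3.7 already allows up to six months of data, which would help.

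**Limits.** A draw removes systematic selection. It does not remove chance imbalance between four and four advisers, or clustering by adviser, for which neither the sample size nor the regression allows. The report should say so.

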#### **3.3 Staff perceptions of the acceptability and feasibility of the training and support, and their knowledge, confidence and skills to use the techniques taught**

##### **3.3.1 Pre and post intervention questionnaires**

The Health Literacy Officer collects pre and post training questionnaire data as part of their practice. This data will be made available to the research team with consent from individual staff undergoing the training. Questionnaire data will be collected,

with consent, from staff from the two participating services who receive the Verbal Health Literacy training. The Health Literacy Officer will also be training staff from other services in Derbyshire Community Health Services and the Local Authority during this time. She will be collecting the same questionnaire data from them.

Therefore, we will ask these additional staff (approximately 60), who receive the Verbal Health Literacy training during the period of the study, to consent to their questionnaire data to be used in the study also. Staff will be asked to complete a short questionnaire at three time points.

1. Baseline data will be collected from staff, via a short questionnaire, prior to their attendance at the training session. The data collected at this stage will include demographic data and ascertain their current knowledge of Verbal Health Literacy techniques and whether they have had Health Literacy training in the past
2. Staff will complete a short questionnaire immediately after they have attended the Verbal Health Literacy training. This will include questions about how useful they found the training and their confidence to use the techniques taught.
3. Staff will complete a final short questionnaire 8 weeks after attending the Verbal Health Literacy training to assess their perceptions of whether they are using the techniques they learnt in their routine care provision, the facilitators and barriers faced and any support they may require helping them use the techniques in their practice.

The questionnaires will be distributed online. This will be via the Derbyshire Community Health Services NHS Foundation Trust Microsoft forms web-based package. The forms will be distributed via the Health Literacy Officer's NHS Microsoft 360 office account. The Health Literacy Officer will share the anonymised, consented data with the lead researcher via email in a password protected spreadsheet.

### **3.3.2 Focus group interviews**

Focus groups will be used to gain deeper and richer insights into participants' experiences and views of the training session itself and the use of the techniques in practice (Kitzinger, 1995). They will allow the staff from the two participating programmes to discuss and debate each other's experiences and views (Kitzinger, 1995). They will focus on wider contextual factors such as why staff receiving and then delivering the intervention may or may not engage with it (Moore *et al.*, 2015). Focus groups will supplement the questionnaires by using open rather than closed questions and encouraging more detailed responses. A topic guide will be used to facilitate the group discussion, but the researcher will be guided by the group's responses and interactions (Kitzinger, 1995) and will probe and dig deeper to understand issues of interest as appropriate (Bryman 2008).

All staff from the two participating services who receive the training will be invited to take part in the focus groups. That is four out of eight Health Intervention Workers from the weight management programme and six physiotherapists and two specialist nurses from the pulmonary rehabilitation programme. The focus groups will take place separately for each service involved. That is there will be one focus group for the weight management service staff and one focus group for the pulmonary rehabilitation staff. This will allow the two groups to discuss together the issues that are important to them specific to their area of practice. The focus groups will take place during timetabled team meeting time, so it has minimum impact on the service and staff time.

The focus groups will be carried out four – six months after attending the Verbal Health Literacy training. They will be carried out face to face or via video call depending on the services preference. Face to face will be recorded using an encrypted audio recorder and the audio files transcribed verbatim. Video call interviews will take place via Google Meet using the researcher's University of Sheffield Google account. The video calls will be recorded and transcribed live using the recording and transcribe functions in Google Meet. The video recording and transcripts will be downloaded from the researcher's University of Sheffield Google

drive immediately after the session and checked and saved on the University of Sheffield secure computer drive. The original recordings will be deleted from the Google drive. All the interview transcripts will be (pseudo)anonymised prior to being analysed.

### **3.4. Assessment of change in how staff use Verbal Health Literacy techniques in practice**

To assess if there is a change in the frequency with which staff use the techniques they have learnt in practice, the lead researcher will observe or record programme sessions before and 12-16 weeks after staff have been trained. The lead researcher will observe the extent to which the Health Literacy techniques 'simple language', 'teach-back' and 'chunk and check' are used. The researcher will attend in person or ask the staff member to record programme sessions on an encrypted recorder. The researcher will use a checklist to describe how often each of the three communication techniques are used: never, sometimes, most of the time, all of the time. All staff from the two services, who will be receiving the training, will be approached for permission to assess two of their sessions (4 staff in the weight loss service and 8 staff in the pulmonary rehabilitation service). If all agree the researcher will observe 24 sessions in total. That is, twelve before they receive the training and twelve after.

Consent will be gained from all staff prior to collecting their data. The focus of this part of the project is on staff behaviour. Service users will be involved incidentally. Even so, verbal consent will also be gained from service users prior to the researcher observing programme sessions.

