#### 3.10.2 Observations

There will be 24 completed checklists for 12 members of staff observed before and after the training. For each health literacy technique, a 2x2 table will be created. This is so we can compare the % of Verbal Health Literacy technique used, most/all of the time versus sometimes/never, pre training and post training. We will make this comparison using McNemar's Test.

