## **6.Timescales**

(Ethics outcome dependent)-

June- July 2024 - Recruitment of staff participants and pre intervention staff observations.

July- August 2024 - Delivery of training package and pre and immediately post intervention staff questionnaires.

July – November 2024 – Recruitment of service users and baseline outcome measures and Health Literacy Questionnaire data collection.

August– February 2025 – Service user post intervention outcome measures and Health Literacy Questionnaire data collection.

September – October 2024 – Two month follow up staff questionnaires.

October – November 2024 – Post intervention staff observations and/or recording of consultations.

November - January 2025 – Staff focus group interviews.

August 2024– March 2025 - Data analysis.

January – March 2025 – Write report/disseminate.

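### Technique use is rated before and after training without masking of the period and without a rule that each staff member's two sessions be observed in the same mode

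*Combined protocol and SAP*

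**What the plan says.** Section 3.4 states that "the lead researcher will observe or record programme sessions before and 12-16 weeks after staff have been trained". The scale is a four-level judgement: "The researcher will use a checklist to describe how often each of the three communication techniques are used: never, sometimes, most of the time, all". The section gives no anchors or thresholds for these categories. On mode, "The researcher will attend in person or ask the staff member to record programme sessions on an encrypted recorder".

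The sample is every staff member due to be trained, "4 staff in the weight loss service and 8 staff in the pulmonary rehabilitation service", with one session before and one after: "If all agree the researcher will observe 24 sessions in total". Untrained staff are not observed.

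Section 3.10.2 dichotomises each rating, "most/all of the time versus sometimes/never, pre training and post training", separately for each technique, and adds: "We will make this comparison using McNemar's Test". It does not say whether the test is exact, continuity-corrected or uncorrected.

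Section 6 lists "Recruitment of staff participants and pre intervention staff observations" for June–July 2024. Post-training sessions fall in October–November 2024, and that entry allows observation, recording or both. Data analysis runs to March 2025.

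The document does not mention masked file labels, scoring order, a second rater, or keeping the same mode at both time points.

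**The concern.** The observations serve objective (c) in section 2.3, which asks whether the training is put into practice. That is the first link in the theory of change in section 1.3.7. The other evidence on use is staff self-report: the 8-week questionnaire (section 3.3.1) and the focus groups (section 3.3.2). If patient outcomes do not move, section 8 promises an account of why, and that account depends on knowing whether staff behaviour changed.

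Two things could shift the contrast without any change in behaviour:

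- **Expectation.** The person leading the evaluation makes an unanchored judgement while able to know that a session is post-training.
- **Mode.** If a staff member is watched in person before training and recorded afterwards, or the reverse, any difference between the modes in what is heard or how staff behave becomes part of the apparent effect.

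**Working it through.** **1. The plan's own count.** (4 + 8) staff × 2 sessions = 24, as stated in sections 3.4 and 3.10.2. This gives 12 pairs per technique.

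**2. How few ratings decide the result.** Let *b* be the pairs that move up across the cut and *c* those that move down. A two-sided 5% level is assumed, since none is stated for this test. With *c* = 0:

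- Exact McNemar, p = 2 × (1/2)^*b*: 5 v 0 gives 0.0625 and 6 v 0 gives 0.031.
- Continuity-corrected, χ² = (|*b* − *c*| − 1)²/(*b* + *c*): 5 v 0 gives 16/5 = 3.2, p = 0.074; 6 v 0 gives 25/6 = 4.17, p = 0.041.
- Uncorrected, χ² = (*b* − *c*)²/(*b* + *c*): 3 v 0 gives 3, p = 0.083; 4 v 0 gives 4, p = 0.046.

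Under any version, one session moved from *sometimes* to *most of the time* can carry a technique across 5%.

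**3. Size of the bias in the percentage.** The documents give no rating distribution and no upgrade rate, so both are assumed. Take never/sometimes/most/all = 40/40/15/5% at both periods, with no true change. A share *u* of post-training ratings is lifted one level. Only a lift from *sometimes* to *most* crosses the cut, so the spurious shift is 0.40 × *u*:

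- *u* = 0.2: 0.40 × 0.2 = 8 points (20% to 28%)
- *u* = 0.3: 0.40 × 0.3 = 12 points (20% to 32%)
- *u* = 0.5: 0.40 × 0.5 = 20 points (20% to 40%)

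This does not depend on the test.

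**4. Effect on the planned test.** If a person's two ratings are independent and *u* = 0.5, then P(up) = 0.80 × 0.40 = 0.32 and P(down) = 0.20 × 0.60 = 0.12. The trinomial probabilities over 12 pairs are summed wherever p < 0.05. The ranges below cover a latent within-person correlation from 0 to 0.7, also assumed:

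| *u* | Exact McNemar | Uncorrected McNemar |
|---|---|---|
| 0 | 0.03–0.4% | 1.5–4.5% |
| 0.2 | 0.3–1.2% | 5.1–7.1% |
| 0.3 | 0.8–2.1% | 9.1–10.0% |
| 0.5 | 3.7–5.8% | 17.2–21.6% |

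With 12 pairs, the continuity-corrected test rejects in the same cases as the exact test in these runs.

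**5. Sensitivity to the bias model.** Suppose instead that a share *u* of all post-training ratings below the cut is moved above it, and that a proportion π is truly above it. The post-training share is then π + (1 − π)*u*. At *u* = 0.5 and independent ratings, exact McNemar gives a false improvement with probability 9.9% for π = 0.5 and 42.6% for π = 0.1. The error rate therefore depends heavily on the assumed form of the bias.

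**The case against.** The strongest reply has four parts.

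- **This is a process measure.** It is neither a primary nor a secondary outcome, and it is triangulated with questionnaires and focus groups in a declared mixed-methods evaluation. That stands and keeps the point minor. A reader might call these ratings the only objective evidence of behaviour change. They are not objective, because they are unanchored judgements. What holds is that no other measure of use is independent of staff self-report.
- **Exact McNemar is conservative here.** Under the step 4 assumptions it stays near or below 5% even with half the sessions upgraded. That stands for those assumptions. A reader might infer a roughly 20% false-positive rate in general, for instance from a paired rank test on the four-level ratings. The plan does not use such a test, and among the McNemar versions in step 4 only the uncorrected one reaches that size. The biased percentage change remains under every version.
- **Compulsory audio has real costs.** Service users' verbal consent in section 3.4 is worded for observation. Pulmonary rehabilitation supplies 8 of the 12 staff, its sessions combine exercise and education, and different staff work with different service users (sections 1.3.6 and 3.2). Attributing speech to one person from audio may be hard. That stands, so requiring audio for all 24 sessions would go too far.
- **Masking is partial.** Speech may reveal the period. Masking also leaves reactivity to being observed or recorded, and time trends with no untrained comparison.

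A reader might also infer that the rater knows the period for every session. For in-person sessions this is certain. For recordings it is inferred from silence: the plan neither says so nor prevents it.

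**Conclusion.** The point holds as a low-severity design improvement. As written, section 3.4 lets expectation and mode differences enter the before/after contrast in section 3.10.2, with 12 pairs and a cut between adjacent subjective categories. The main harm is a biased change in the percentage rated above the cut: about 8, 12 or 20 points if 20%, 30% or 50% of post-training sessions are rated one level too high. That rests on the assumed 40/40/15/5% distribution and upgrade rates. The effect on the false-positive rate is secondary. At 50% upgrading it is about 4–6% (exact) or 17–22% (uncorrected), and it is sensitive to the bias model. The documents do not show that bias will occur or how large it would be; they show only that nothing guards against it.

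**What to change.** Amend section 3.4 as follows.

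1. Use the same mode, in person or audio, for both sessions of each staff member. Prefer audio where consent and attribution of speech allow.
2. For recorded pairs, have the staff member make the recording without the lead researcher present, and leave the pre-training files unscored.
3. Have another existing team member remove dates and relabel the files. The lead researcher then scores them in random order after the last post-training recording and, where possible, before the focus groups. The rater notes a guess of the period for each file.
4. Flag pairs rated in person as unblinded when reporting. If pre-training sessions have already been observed in person, keep that mode afterwards and report the limitation.

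Section 3.10.2 should also name the version of McNemar's test.

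**Cost.** The wording changes, relabelling of at most 24 files, and a check that service-user consent covers recording. Scoring is deferred, which fits the analysis window to March 2025, although focus groups begin in November 2024 and the order needs managing. Masking may be incomplete, and some pulmonary rehabilitation pairs may have to stay in person. No extra assessor is needed and the number of sessions is unchanged.
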